7.3 Safety Set

The safety set (SAF) will include all subjects who have received at least one dose of the study drug. Subjects in the SAF will be analyzed as treated.

8. General Statistical Considerations

8.1 Unit of Analysis

The study eye will be used for all monocular analyses. The fellow eye will inherently be included in all binocular analyses. Both eyes will be displayed and analyzed for all ophthalmic safety endpoints.

The study eye will be defined by the study Investigator as the eye that meets all enrollment criteria. If both eyes meet all enrollment criteria, then the eye with the worse Visit 2 pre-treatment/baseline BDCVA at 40 cm (Precision Vision chart) will be the study eye. If both eyes have the same BDCVA at 40 cm, the right eye will be the study eye.

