### 10.4 Unit of Analysis

The study eye will be used for all monocular analyses. The fellow eye will inherently be included in all binocular analyses. Both eyes will be displayed and analyzed for all ophthalmic safety variables.

The study eye will be defined by the study Investigator as the eye that meets all enrollment criteria. If both eyes meet all enrollment criteria, then the eye with the worse Visit 2 pre-treatment/baseline BDCVA at 40 cm (Precision Vision chart) will be the study eye. If both eyes have the same BDCVA at 40 cm, the right eye will be the study eye.

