3.1 Overall Study Design

This is a four-visit multi-center, randomized, double-masked, parallel-group study evaluating the safety and efficacy of CSF-1 compared with Vehicle in approximately 300 subjects with presbyopia. The study design is summarized in Figure 1.

Visit 1 (Screening, Day -14 to -1): Qualified subjects will receive 1 drop of Vehicle instilled in each eye, followed by preliminary efficacy assessments to identify Vehicle responders at 15 minutes post-vehicle instillation.

Vehicle responder is defined as a subject who had a > 0.14 LogMAR (i.e., 7 letters) improvement in post-Vehicle treatment (at 15 minutes post-Vehicle treatment) monocular BDCVA in either eye at 40 cm

compared to Visit 1 pre-treatment, or a > 0.14 LogMAR (i.e., 7 letters) improvement in monocular BDCVA in either eye at 40 cm between Visit 1 (pre-treatment) and Visit 2 (pre-treatment baseline).

Visit 2 (Day 1): Baseline assessments. Subjects who meet all inclusion and none of the exclusion criteria and qualify as Vehicle non-responders, will be randomized 1:1 to one of the following treatment arms:

- CSF-1 (0.4% pilocarpine hydrochloride ophthalmic solution)
- Vehicle

Pre-treatment measurements taken at this visit are considered as baseline.

[figure not shown]
At the Visit 2 (Day 1) clinic visit, study personnel will instill Dose 1 of study drug at 8:30 AM \pm 30 minutes in each eye. Efficacy and safety assessments will be conducted for 2 hours following Dose 1. Dose 2 will be instilled by study personnel at 10:30 AM \pm 30 minutes in each eye. Efficacy and safety assessments will be conducted for 4 hours following Dose 2.

All subjects will be instructed to dose twice daily (BID) with a single drop in each eye for approximately 1 week. The first daily dose should occur in the morning, with the second dose following 2 hours later (± 1 hour). Subjects will be instructed not to dose at home on clinic visit days.

Visit 3 (Day 8): Study personnel will instill Dose 1 of study drug at 8:30 AM \pm 30 minutes in each eye. Efficacy and safety assessments will be conducted for 2 hours following Dose 1. Dose 2 will be instilled by study personnel at 10:30 AM \pm 30 minutes in each eye. Efficacy and safety assessments will be conducted for 2 hours following Dose 2.

[figure not shown]

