8.3 Definition of Baseline

For all endpoints, baseline is defined as the pre-randomization measurement taken at Visit 2 (Day 1). If the measurement is not available from Visit 2 (Day 1), then the measurement from Visit 1 (Day -14 to -1) will be used as baseline. Change from baseline will be calculated as: Post-Baseline Measure – Baseline Measure.

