8.4 Data Analysis Conventions

All data analysis will be performed by SDC after the study is completed and the database has been locked and released for unmasking. Statistical programming and analyses will be performed using SAS® Version 9.4 or higher. Output will be provided in rich text format for tables and portable document format for tables, listings, and figures using landscape orientation. All study data will be listed by subject, treatment, and visit (as applicable) based on all randomized subjects unless otherwise specified.

Summaries for continuous and ordinal variables will include the number of observations, arithmetic mean, standard deviation (SD), median, minimum, and maximum. Minima and maxima will be reported with the same precision as the raw values; means and medians will be presented to 1 additional decimal place than reported in the raw values. Standard deviations will be presented to 2 additional decimal places than reported in the raw values. Summaries for discrete variables will include frequency counts and percentages. All percentages will be rounded to 1 decimal place (i.e., XX.X%). Change from baseline will be calculated as baseline subtracted from the relevant post-baseline visit (Post-Baseline Visit – Baseline Visit), with baseline defined in Section 8.3 of this SAP.

Gains or improvements in BDCVA at 40 cm (Precision Vision chart) of \geq 3-lines (15-letters) are defined as changes from baseline in BDCVA at 40 cm (Precision Vision chart) of \leq -0.30 logMAR (e.g., -0.30, -0.32, ... logMAR).

Gains or improvements in BDCVA at 40 cm (Precision Vision chart) of \geq 2-line (10-letters) are defined as changes from baseline in BDCVA at 40 cm (Precision Vision chart) of \leq -0.20 logMAR (e.g., -0.20, -0.22, ... logMAR).

[figure not shown]
Similarly, loss in BDCVA of \geq 5 letters (ETDRS at 4 m) are defined as changes from baseline in BDCVA (ETDRS at 4 m) of \geq 0.10 logMAR (e.g., 0.10, 0.12, ... logMAR).

All statistical tests, unless otherwise indicated, will be 2-sided with a significance level of 0.05 ($\alpha = 0.05$). Confidence intervals (CI) for differences between treatment groups will be 2-sided at 95% confidence. All p-values will be rounded to 4 decimal places; p-values less than 0.0001 will be presented as " <0.0001 "; p-values greater than 0.9999 will be presented as " >0.9999 ." Unless otherwise specified, summaries will be presented by treatment group and, where appropriate, visit.

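### Choosing the study eye on the same Visit 2 near reading that serves as baseline overstates the responder percentages in both arms, while leaving the test and the odds ratio essentially intact

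*SAP*

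**What the plan says.** SAP 8.1 starts from eligibility: "The study eye will be defined by the study Investigator as the eye that meets all enrollment criteria". When both eyes are eligible, "then the eye with the worse Visit 2 pre-treatment/baseline BDCVA at 40 cm (Precision Vision chart) will be the study eye". Ties go to the right: "If both eyes have the same BDCVA at 40 cm, the right eye will be the study eye". Protocol 10.4 has the same rule ("If both eyes meet all enrollment criteria, then the eye with the worse Visit 2 pre-treatment/baseline BDCVA at 40 cm").

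SAP 8.3 then fixes the reference value: "For all endpoints, baseline is defined as the pre-randomization measurement taken at Visit 2 (Day 1"), with Visit 1 used only if Visit 2 is missing, and "Change from baseline will be calculated as: Post-Baseline Measure – Baseline Measure". SAP 8.4 sets the near-acuity part of response: a 3-line gain is "defined as changes from baseline in BDCVA at 40 cm (Precision Vision chart) of" -0.30 logMAR or lower. So one Visit 2 reading both selects the eye and anchors the gain.

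SAP 3.1 adds a screening limit on the same reading. A subject counts as a Vehicle responder, and is not randomised, after a change of more than 0.14 logMAR (7 letters) that is an "improvement in monocular BDCVA in either eye at 40 cm between Visit 1 (pre-treatment) and Visit 2 (pre-treatment baseline"). There is no matching limit for worsening.

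The four sensitivity analyses in SAP 12.2 concern missing data and the per-protocol set. No visible text varies the baseline or the choice of eye.

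**The concern.** Each acuity reading is true acuity plus error. If two eyes have similar true near acuity, the one that reads worse on a given day is often the one with the unlucky error. On Day 8 the error is drawn afresh, so that eye improves on average without any drug effect. The run-in limit works in the same direction: it removes subjects whose Visit 2 reading was unusually good compared with Visit 1 and keeps those whose reading was unusually poor.

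The endpoint is a fixed cut at 15 letters, which the protocol's criteria for effectiveness treat as clinically meaningful. A baseline that is a letter or two too poor moves subjects with smaller real gains over that cut. The endpoint is itself a percentage, and H01 to H04 are worded as differences in percentages. What is at stake is how large the reported responder rates are and what they mean.

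**Working it through.** **Inputs from the documents.** 140 per arm, 42.5% against 17.5%, two-sided 0.05, Pearson chi-squared, power stated as above 97.5% (Protocol 10.5, SAP 5); the eye, baseline, response and run-in rules above; logistic regression with baseline 40 cm BDCVA as covariate (SAP 12.1).

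**Assumed inputs (not in the documents).** SD of one reading, s = 2-5 letters; SD of the true between-eye difference, d = 0-6 letters; SD of true gain 5-7 letters; 50% or 100% of subjects with both eyes eligible.

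**1. The plan's own figure.** Mean rate = (0.425 + 0.175)/2 = 0.30. SE under the null = sqrt(2 × 0.30 × 0.70/140) = 0.0548. SE under the alternative = sqrt((0.425 × 0.575 + 0.175 × 0.825)/140) = 0.0527. z = (0.25 - 1.96 × 0.0548)/0.0527 = 2.71, so power is 99.7%. The stated bound holds.

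**2. Mean error in the selected baseline.** The observed between-eye difference has variance d² + 2s². Taking the worse eye gives a mean error of s² × sqrt(2/π)/sqrt(d² + 2s²) letters in the poor direction. For s = 3, d = 3: 9 × 0.798/sqrt(27) = 1.38.

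| s | d = 0 | d = 3 | d = 6 |
|---|---|---|---|
| 2 | 1.13 | 0.77 | 0.48 |
| 3 | 1.69 | 1.38 | 0.98 |
| 4 | 2.26 | 1.99 | 1.55 |
| 5 | 2.82 | 2.60 | 2.15 |

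These are for all subjects with both eyes eligible and no run-in limit. With half eligible they halve (lowest 0.24). With the run-in limit applied the highest rises to 3.33.

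**3. Responder rates.** Simulation of 1,000,000 subjects per setting, whole-letter readings, right eye on ties, near-acuity part of the endpoint only. Reading (a) takes 42.5%/17.5% as rates in a pre-fixed eye with no run-in limit and adds the rule. Reading (b) takes them as already containing the artefact and removes it. The last two columns belong to (b).

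| Setting | Baseline too poor by | (a) rates | (b) rates | Difference | Power, 140 per arm |
|---|---|---|---|---|---|
| Mild: gain SD 7, s 2, d 6, half eligible, no run-in | 0.24 | 43.8 / 18.3 | 41.2 / 16.7 | 24.5 | 99.6% |
| Middle: gain SD 5, s 3, d 3, all eligible, no run-in | 1.4 | 50.8 / 23.0 | 34.7 / 13.0 | 21.7 | 99.1% |
| Extreme: gain SD 5, s 5, d 0, all eligible, run-in | 3.33 | 58.2 / 27.6 | 28.8 / 10.5 | 18.4 | 97.5% |

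The direction was the same in every setting tried. Power touches the stated bound only in the extreme corner, where the simulated run-in also excludes about 41% of subjects.

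**4. Odds ratio.** As planned: (0.425/0.575)/(0.175/0.825) = 3.48. From the (b) rates: mild (0.412/0.588)/(0.167/0.833) = 3.50; middle (0.347/0.653)/(0.130/0.870) = 3.56; extreme (0.288/0.712)/(0.105/0.895) = 3.45. It hardly moves.

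**5. Type I error.** In 1,500 simulated null trials analysed with the planned covariate model, rejection was 4.5% (simulation error about 0.5 points).

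**6. Choosing the eye on Visit 1 instead.** With gain SD 5, s = 4, d = 2, all eligible, run-in applied and the plan calibrated to 42.5%/17.5%, the baseline error falls from 2.4 to 0.7 letters, the rates become 33.8%/12.6% (difference 21.2 points), and the odds ratio is (0.338/0.662)/(0.126/0.874) = 3.54. Over s = 3-5 and d = 2-4 the remaining error is 0.3-1.2 letters.

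**The case against.** The strongest reply is that nothing decisive changes. The eye is chosen before treatment by an explicit, deterministic rule that is the same in both arms. The Vehicle arm shows the same drift. Baseline is a covariate, and SAP 12.1 reports a p-value and an odds ratio, not a risk difference. All of that stands. A reader might infer that the trial could succeed on an artefact, that the treatment effect is inflated on every scale, or that the sample size is too small. The documents do not support any of these: steps 1, 3, 4 and 5 show the stated power met, the odds ratio stable and type I error not raised.

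The risk difference is also unbiased for the eye that the plan defines. It is overstated only relative to an eye chosen independently of baseline error. That is correct, and it is how the point is put here. It still matters, because the endpoint is a percentage, H01 to H04 are differences in percentages, and Protocol 10.7 lists marginal proportions and their difference. The baseline covariate does not remove the artefact from the raw rates.

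The size is open to challenge, and fairly so. No test-retest SD, between-eye SD or share with both eyes eligible is given; several eligibility criteria are redacted; and the simulation omits the 4 m no-loss condition. The Phase 2 study-eye rule is not stated, so it is unknown whether 42.5% and 17.5% already contain the artefact. Finally, Visit 1 is not a fully independent reading, because the run-in limit ties it to Visit 2.

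**Conclusion.** The point holds as a matter of estimation. When both eyes qualify and read differently, the plan's baseline is too poor on average, and the 15-letter responder percentages are overstated in both arms, as is their difference in percentage points. The direction needs only that readings carry error. The size rests on the assumed ranges: about 0.2-3.3 letters. If the planned rates contain the artefact, they would be about 29-41% and 11-17% without it, with a difference of 18-24 points. There is no worse-eye selection where only one eye qualifies or the eyes tie, and the documents do not say how common those cases are.

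It would go too far to say that the planned rates are shown to be inflated, or that the superiority test is compromised. This is a cheap improvement to what the percentages mean, not a threat to the trial's conclusion.

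**What to change.** In Protocol 10.4 and SAP 8.1: if both eyes meet all criteria, take the eye with the worse Visit 1 pre-treatment 40 cm BDCVA, the right eye if equal, and keep Visit 2 as baseline. The run-in rule already needs that Visit 1 reading in each eye, so this costs one sentence per document and no new measurement. It removes most but not all of the bias, because the run-in limit links the two visits. In any subject whose Visit 2 reading is missing and whose baseline falls back to Visit 1, the problem would return. The price is somewhat less favourable reported rates.

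If eyes have already been chosen under the current rule, do not use the average of Visits 1 and 2 as baseline to isolate the artefact. Averaging also lowers baseline noise and moves the rates by itself: in a simulation with a pre-fixed eye and no run-in limit (s = 4), it took 31.0%/11.3% to 28.3%/9.1% and the odds ratio from about 3.5 to about 4. Instead report, as supportive, the H01 to H04 responder rates in the eye with the worse Visit 1 reading, among subjects with both eyes eligible, where post-dose monocular readings exist for both eyes. State in the clinical study report that the absolute responder rates include regression to the mean.

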8.2 Missing Data Handling and Sensitivity Analysis

The primary efficacy analysis and the key secondary analyses will be performed on the FAS, as described in section 12.1. In the event of missing data, the primary imputation method will be Multiple Imputation (MI), using randomized treatment-based Markov Chain Monte Carlo (MCMC). Sensitivity analyses will also be performed on the primary and key secondary efficacy endpoints measured at Visit 3 (Day 8). These sensitivity analyses will be considered supportive of the primary and key secondary analyses.

8.3 Definition of Baseline

For all endpoints, baseline is defined as the pre-randomization measurement taken at Visit 2 (Day 1). If the measurement is not available from Visit 2 (Day 1), then the measurement from Visit 1 (Day -14 to -1) will be used as baseline. Change from baseline will be calculated as: Post-Baseline Measure – Baseline Measure.

8.4 Data Analysis Conventions

All data analysis will be performed by SDC after the study is completed and the database has been locked and released for unmasking. Statistical programming and analyses will be performed using SAS® Version 9.4 or higher. Output will be provided in rich text format for tables and portable document format for tables, listings, and figures using landscape orientation. All study data will be listed by subject, treatment, and visit (as applicable) based on all randomized subjects unless otherwise specified.

Summaries for continuous and ordinal variables will include the number of observations, arithmetic mean, standard deviation (SD), median, minimum, and maximum. Minima and maxima will be reported with the same precision as the raw values; means and medians will be presented to 1 additional decimal place than reported in the raw values. Standard deviations will be presented to 2 additional decimal places than reported in the raw values. Summaries for discrete variables will include frequency counts and percentages. All percentages will be rounded to 1 decimal place (i.e., XX.X%). Change from baseline will be calculated as baseline subtracted from the relevant post-baseline visit (Post-Baseline Visit – Baseline Visit), with baseline defined in Section 8.3 of this SAP.

Gains or improvements in BDCVA at 40 cm (Precision Vision chart) of \geq 3-lines (15-letters) are defined as changes from baseline in BDCVA at 40 cm (Precision Vision chart) of \leq -0.30 logMAR (e.g., -0.30, -0.32, ... logMAR).

Gains or improvements in BDCVA at 40 cm (Precision Vision chart) of \geq 2-line (10-letters) are defined as changes from baseline in BDCVA at 40 cm (Precision Vision chart) of \leq -0.20 logMAR (e.g., -0.20, -0.22, ... logMAR).

[figure not shown]
Similarly, loss in BDCVA of \geq 5 letters (ETDRS at 4 m) are defined as changes from baseline in BDCVA (ETDRS at 4 m) of \geq 0.10 logMAR (e.g., 0.10, 0.12, ... logMAR).

All statistical tests, unless otherwise indicated, will be 2-sided with a significance level of 0.05 ($\alpha = 0.05$). Confidence intervals (CI) for differences between treatment groups will be 2-sided at 95% confidence. All p-values will be rounded to 4 decimal places; p-values less than 0.0001 will be presented as " <0.0001 "; p-values greater than 0.9999 will be presented as " >0.9999 ." Unless otherwise specified, summaries will be presented by treatment group and, where appropriate, visit.

8.5 Adjustment for Multiplicity

If the primary null hypothesis, H_{01} , is rejected at a 2-sided alpha = 0.05 in favor of CSF-1 in the alternative hypothesis, H_{11} , tested as delineated in the primary efficacy analysis section ([Section 12.1](#)), then the study will be considered a success and the following key secondary hypotheses will be tested in hierarchical order, each at a 2-sided alpha = 0.05, where inference will be made on each null hypothesis only if the prior null hypotheses are rejected in favor of CSF-1.

1. Visit 3 (Day 8), 2 hours following Dose 1 (H_{02})
2. Visit 3 (Day 8), 1 hour following Dose 2 (H_{03})
3. Visit 3 (Day 8), 2 hours following Dose 2 (H_{04})

9. Disposition of Subjects

Subject disposition will be presented in terms of the numbers and percentages of subjects who were randomized, completed the study, and discontinued from the study. A discontinued subject is someone who does not complete the 4 protocol-defined study visits. Subjects who are not discontinued from the study will be considered study completers. Disposition will be summarized by treatment arm for all randomized subjects. The reasons for study discontinuation will also be summarized and include: AE, lost to follow-up, physician decision, protocol violation, study terminated by sponsor, withdrawal by subject, death, and other. A subject listing will be provided which includes the date and reason for study discontinuation.

The number of subjects in each of the analysis sets (FAS, PPS, and SAF) will be displayed by treatment arm, with the number of subjects and percentages calculated using randomized subjects as the denominator. The number and percentage of subjects with any (major, or minor) protocol deviations will be summarized by treatment arm and overall for all randomized subjects. Protocol deviations will be classified as major or minor prior to the closure of the database during a masked review of each protocol deviation. Major deviations will be defined as those deviations that potentially affect the analysis of the primary study endpoint.

A subject listing will be provided which includes the date of the deviation, the deviation code and description, and the classification of whether the deviation was deemed major or minor. In addition, subject listings will include treatment arm and ICF signature date, and exclusions from the PPS. There will also be a listing of screen failures.

10. Demographic and Baseline Characteristics

10.1 Demographics

Subject demographic data collected in this study, age, sex, race, ethnicity, and childbearing potential. Subjects who record more than one race will be grouped into a single category denoted as multi-racial, and subjects who record more than one iris color (study eye) will be classified as heterochromia. Sex, race, ethnicity, childbearing potential, and iris color will be presented using descriptive summary statistics with frequency counts and percentages. Age (years) will be summarized with continuous descriptive statistics. Categorical variables will be summarized with number and percentage.

Demographic variables along with two baseline characteristics, iris color of study eye and manifest refraction spherical equivalent (MRSE), will be summarized for the FAS and PPS by treatment arm and overall in tables. A subject listing that includes all summarized demographic and baseline variables will also be provided.

10.2 Baseline Characteristics

Baseline characteristics are measured to ensure the safety and eligibility of subjects at Visit 1 (Day -14 to -1). Subject level listings will be used to present pre-treatment information from the FAS at the eye level when appropriate. Baseline characteristics will be contained in subject listings only and will include:

- Manifest refraction
- Iris color
- Dark-adapted pupillometry
- Fluorescein staining
- Dilated indirect funduscopy

11. Medical History and Concomitant Medications

11.1 Medical History

Medical history will be coded using Medical Dictionary for Regulatory Activities (MedDRA) Version 23.0. Non-ocular medical history will be summarized using discrete summary statistics and presented by treatment arm at the subject level by System Organ Class (SOC) and Preferred Term (PT) using the SAF. Ocular medical history will be similarly summarized at the subject level. If a subject reports the same PT multiple times within the same SOC, then that PT will only be reported once within that SOC. As with the PT, if a subject reports multiple conditions within the same SOC, then that SOC will only be reported once. All SOC and PTs within an SOC category will be ordered by descending frequency based on all subjects.

Listings of medical history will be generated separately for ocular and non-ocular information.

